## 7. APPENDICES

### 7.1. Appendix A: Table shells

The list of planned outputs and table shells will be presented in a separate document.

### 7.2. Appendix B: R Example Code

#### 7.2.1. Example Data Formats for First Event and Recurrent Events

Example dataset for time to first outcome:

ptid	tstart	tstop	pcv13	ipd	x1	x2	xt1	xt2	censor	endfu
1001	-1	0	0	0	1	0	0	0	0	87
1001	0	30	0	0	1	0	0	0	0	87
1001	30	60	1	0	1	0	1	0	0	87
1001	60	87	1	0	1	0	1	0	1	87
1002	-1	0	0	0	0	0	0	0	0	45
1002	0	30	0	0	0	0	0	1	0	45
1002	30	45	0	1	0	0	1	1	0	45

Example dataset including any subsequent outcomes:

ptid	tstart	tstop	pcv13	ipd	x1	x2	xt1	xt2	censor	endfu2
1001	-1	0	0	0	1	0	0	0	0	87
1001	0	30	0	0	1	0	0	0	0	87
1001	30	60	1	0	1	0	1	0	0	87
1001	60	87	1	0	1	0	1	0	1	87
1002	-1	0	0	0	0	0	0	0	0	106
1002	0	30	0	0	0	0	0	1	0	106
1002	30	45	0	1	0	0	1	1	0	106
1002	45	60	0	0	0	0	1	1	0	106
1002	60	84	0	1	0	0	1	1	0	106
1002	84	90	0	0	0	0	1	1	0	106
1002	90	106	0	0	0	0	1	1	0	106

Where:

- *ptid*: patient identifier
- *tstart*: first day of interval. -1 represents baseline period
- *tstop*: last day of interval
- *pcv13*: binary indicator for time-varying PCV13 vaccination status (exposure)
- *ipd*: binary indicator for IPD event (outcome)
- *x1, x2, ..., xn*: time-fixed confounders
- *xt1, xt2, ..., xtn*: time-varying confounders
- *censor*: binary indicator for censoring event

- *endfu*: last day of follow-up up to any first event
- *endfu2*: last day of follow-up

For binary variables, 1 indicates Yes, 0 indicates No. Note, all variables in dataset must be numeric for the *ipwtn* function.

### 7.2.2. Code for Generating IPTW and IPCW

```
library(ipw)
iptw <- ipwtn(exposure = pcv13, family = "survival",
numerator = ~ x1 + x2 + ... + xn, denominator = ~ x1 + x2 + ... + xn + xt1 + xt2 + ... + xtn,
id = ptid, tstart = tstart, timevar = tstop, type = "first",
data = ipdfirst)
ipcw <- ipwtn(exposure = censor, family = "survival",
numerator = ~ x1 + x2 + ... + xn, denominator = ~ x1 + x2 + ... + xn + xt1 + xt2 + ... + xtn,
id = patient, tstart = tstart, timevar = tstop, type = "cens",
data = ipdfirst)
iptw.stab<-iptw$ipw.weights
ipcw.stab<-ipcw$ipw.weights
ipdfirst<-cbind(ipdfirst, iptw.stab, ipcw.stab)
ipdfirst$comb.weights<- ipdfirst$iptw.stab*ipdfirst$ipcw.stab

#Plot of stabilized weights during follow-up in unvaccinated
ipwplot(weights = subset(ipdfirst$iptw, ipdfirst$pcv13==0),
subset(timevar = ipdfirst$tstop, ipdfirst$pcv13==0),
binwidth = 183, ylim = c(-1.5, 1.5), main = "Stabilized weights",
xlab = "Years Since Index", ylab = "Logarithm of Stabilized IPTW",
xaxt = "n", yaxt = "n")
axis(side = 1, at = seq(0, 15, 1), labels = as.character(seq(0, 15, 1)*0.5))
axis(side = 2, at = c(-1.5, -1, -0.5, 0, 0.5, 1, 1.5),
labels = as.character(c(-1.5, -1, -0.5, 0, 0.5, 1, 1.5)))
```

### 7.2.3. Code for Incidence Rates

```
#First events
ipdfirst$py <- ifelse(ipdfirst$tstart>=0,
(ipdfirst$tstop - ipdfirst$tstart)/365.25, 0)
ipdfirst$lnpy <- ifelse(ipdfirst$tstart>=0, log(ipdfirst$py), 0)
#Rate in unvaccinated

fit_erate_unvac <- glm(event ~ pcv13 + offset(lnpy), family=poisson(link="log"),
subset(ipdfirst[ipdfirst$tstart>=0, ]))
summary(fit_erate_unvac)
exp(coef(fit_erate_unvac)[1])
```

```
exp(confint(fit_erate_unvac))
#Rate in vaccinated (where pcv13 is factor)
fit_erate_vac <- glm(event ~ relevel(pcv13, ref= "1") + offset(lnpy),
  family= poisson(link="log"), subset(ipdfirst[ipdfirst$tstart>=0, ]))
summary(fit_erate_vac)
exp(coef(fit_erate_vac)[1])
exp(confint(fit_erate_vac))

#Recurrent events
library("sandwich")
library("lmtest")
#Rate in unvaccinated
fit_erate_rec_unvac <- glm(event ~ pcv13 + offset(lnpy), family=poisson(link="log"),
  subset(ipdrec[ipdrec$tstart>=0, ]))
fit_clust_rec_unvac <- coeftest(fit_erate_rec_unvac, vcov. = vcovCL(fit_erate_rec_unvac,
  cluster = ipdrec$patid, type = "HC0"))
fit_clust_rec_unvac
exp(coef(fit_clust_rec_unvac)[1])
exp(confint(fit_clust_rec_unvac))

#Rate in vaccinated (where pcv13 is factor)
fit_erate_rec_vac <- glm(event ~ relevel(pcv13, ref= "1") + offset(lnpy),
  family=poisson(link="log"), subset(ipdrec[ipdrec$tstart>=0, ]))
fit_clust_rec_vac <- coeftest(fit_erate_rec_vac, vcov. = vcovCL(fit_erate_rec_vac,
  cluster = ipdrec$patid, type = "HC0"))
fit_clust_rec_vac
exp(coef(fit_clust_rec_vac)[1])
exp(confint(fit_clust_rec_vac))
```

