## 1. AMENDMENTS FROM PREVIOUS VERSION(S)

Version	Date	Changes	Rationale
1.3	07-Dec-2023	Added 'in the United States' to the title	Reflect protocol amendment
1.3	07-Dec-2023	Added age group and PPSV23 number of doses as potential stratification variables	Reflect protocol amendment
1.3	07-Dec-2023	Updated potential negative control outcomes	Reflect protocol amendment
1.3	07-Dec-2023	Updated opportunistic infections list	Reflect protocol amendment
1.3	07-Dec-2023	Study follow-up now begins six months after the first HIV-related ICD-9-CM or ICD-10-CM code	Reflect protocol amendment
1.3	07-Dec-2023	Removed requirement for six months of continuous enrollment before members' first HIV-related ICD-9-CM or ICD-10-CM code, updated inclusion start date and removed exclusion for individuals with evidence of ART therapy during baseline period	Reflect protocol amendment
1.2	10-Aug-2023	Updated to SOP template version 3.0	
1.2	10-Aug-2023	Added alternate definition of outpatient	Reflect protocol amendment

		candidiasis infection and NDC table	
1.2	10-Aug-2023	Added time-varying covariates for annual HIV viral load testing and annual CD4 cell count testing and their CPT codes. Added time-varying covariates for respiratory virus season.	Reflect protocol amendment
1.2	10-Aug-2023	Study follow-up now begins 90 days after index and at least 90 days of continuous enrolment in medical plans is added to the inclusion criteria	Reflect protocol amendment
1.2	10-Aug-2023	The two outpatient HIV-related codes are now no more than 730 days apart	Reflect protocol amendment
1.2	10-Aug-2023	90 instead of 30-day intervals now used for the analysis of RZV	Needed due to low numbers of patients vaccinated with RZV overall and in each interval
1.2	10-Aug-2023	Updated person-time exclusion in Incidence Rates subsection of 7.1 from 29 to 89 days	Needed to reflect the previous update to the number of days separating recurrent events from 30 to 90 days
1.2	10-Aug-2023	Added a definition of overall SMD	Needed for reporting in output table
1.2	10-Aug-2023	Specified cluster robust standard errors for the 95% confidence intervals for the incidence rates based on recurrent events and updated R code	Needed to account for multiple events per patient

1.2	10-Aug-2023	Updated Payor categories in Table 5.2	Previous categories did not accurately represent the values in the database

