#### **5.8.6. Incidence Rates**

Incidence rates will be reported using first episodes only and again after including recurrent episodes of the same type. Crude incidence rates and 95% CIs will be presented as episodes per 100,000 person-years by PCV13 vaccination status for each outcome overall as well as annually and during time periods of interest (0-3, 3-5 and 5-7 years).

For incidence rates based on first episodes only, the total unvaccinated person-time will be calculated as time from index date to the earliest of the following: outcome, 13 days after their PCV13 vaccination, death, end of health plan enrolment or end of study period. The

total vaccinated person-time will be calculated as time from 14 days after their PCV13 vaccination date or index date, if they were vaccinated more than 13 days before the end of the baseline period, to the earliest of the following: outcome, death, end of health plan enrolment or end of study period.

For incidence rates including recurrent episodes of the same type (separated by at least 90 days), the total unvaccinated person-time will be calculated as time from index date to the earliest of the following: 13 days after their PCV13 vaccination, death, end of health plan enrolment or end of study period. The total vaccinated person-time will be calculated as time from 14 days after their PCV13 vaccination date or index date, if they were vaccinated more than 13 days before the end of the baseline period ,to the earliest of the following: death, end of health plan enrolment or end of study period. Person-time will exclude any time the patient is not at risk, i.e. the first 89 days after an episode. Cluster robust standard errors will be used in the calculation of 95% confidence intervals to account for multiple events per patient.

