### 7.2.5. Code for Cox Models

```
#Code is the same for first event and recurrent events (Andersen-Gill) models
#Crude overall
library(survival)
crude.cox<-coxph(Surv(tstart, tstop, ipd) ~ pcv13 + cluster(ptid), data = ipdfirst)
```

```
#IPT weighted overall
iptw.cox<-coxph(Surv(tstart, tstop, ipd) ~ pcv13 + x1 + x2 + cluster(ptid),
                  data = ipdfirst), weights = iptw.stab
```

```

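### The example code for recurrent-event rates can silently drop the patient clustering that SAP 5.8.6 requires, because it names an identifier (patid) that the SAP's data layout does not contain

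*SAP*

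**What the plan says.** For incidence rates that include repeat episodes, SAP 5.8.6 states: "Cluster robust standard errors will be used in the calculation of 95% confidence intervals to account for multiple events per patient". The SAP's amendment log for version 1.2 records the same intention and says that the code was changed to match: "Specified cluster robust standard errors for the 95% confidence intervals for the incidence rates based on recurrent events and updated R code".

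SAP 7.2.1 sets out the data layout and its variable list gives "ptid*: patient identifier". Neither example dataset has a column called `patid`.

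SAP 7.2.3 fits the recurrent-event rate model to post-index rows only, "subset(ipdrec[ipdrec$tstart>=0" and so on, and then asks for a clustered covariance matrix with "cluster = ipdrec$patid". It does this twice, once for the unvaccinated rate and once for the vaccinated rate. The Cox code in SAP 7.2.5 uses the documented name: "pcv13 + cluster(ptid), data = ipdfirst". SAP 5.8.4 and the title of Appendix 7.2 both label the code as an example.

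**The concern.** The text and the code disagree on the variance estimator. In R, asking a data frame for a column that it does not have returns NULL, and the clustering function accepts NULL as a request for no grouping. A coding slip usually announces itself. This one can produce intervals that look normal but carry no within-patient correction.

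At stake are the 95% intervals of the crude recurrent-event rates by vaccination status, which SAP 5.8.6 plans overall, annually and for 0-3, 3-5 and 5-7 years. SAP 5.8.12 plans the same kind of rate for the negative control outcomes, so these are exposed too if the code is reused there. If patients differ in their underlying risk, row-level intervals are too narrow.

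**Working it through.** The documents give no interval or standard error for these rates, so there is no planned figure to reproduce. The check has two parts: what the code does, and how much it matters at the SAP's own rates.

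**Identifier names in Appendix 7.2**

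- 7.2.1 layout: `ptid`
- 7.2.2 treatment weights: `ptid`; censoring weights: `patient`
- 7.2.3 recurrent rates: `patid` (both calls)
- 7.2.5 Cox models: `ptid`

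**What the code does (R 4.3.3, sandwich 3.1.1)**

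1. On the SAP's own recurrent example dataset, `ipdrec$patid` is NULL. The block does not reach the clustering step: the model asks for `event`, while the layout calls the outcome `ipd`. In addition, `lnpy` is created only for `ipdfirst`.
2. With `event` and `lnpy` supplied, the block was run on test data in the SAP layout: 4,000 patients, one baseline row and thirty 30-day intervals each, and an assumed frailty variance of 2. Standard errors of the log unvaccinated rate:
   - `patid`, as written: 0.0214, no error and no warning
   - one cluster per row, set explicitly: 0.0214, identical covariance matrix
   - `ptid` taken from the whole of `ipdrec`: stops with a length mismatch
   - `ptid` restricted to `tstart >= 0`: 0.0338
3. The ratio is 0.0338/0.0214, or 1.57 from the unrounded values. The 95% interval for the rate per person-year is 0.302-0.328 as written and 0.295-0.336 with clustering. The event rate here was set high to show the mechanism, so this is not an estimate of size.
4. The mismatch arises because the model drops the baseline rows (`tstart = -1`) and the cluster vector does not. In the SAP's example that is 11 rows against 9.

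**Size over full follow-up**

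Inputs from SAP 5.2.3: 5,487 (all-cause pneumonia) and 183 (IPD) per 100,000, 4% annual censoring, 97 months. From SAP 5.3.1 and 5.8.6: the 90-day episode rule. The frailty variance θ is an assumption. The simulation had 60,000 patients in 30-day records. With residual s = y − λt for each row and D events in all, the row-level SE is √(Σ s²)/D. The patient-level SE is √(Σ over patients of (Σ s)²)/D. Intervals are too narrow by 1 − 1/ratio, and the nominal 95% interval covers 2Φ(1.96/ratio) − 1.

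| θ | All-cause SE, row / patient | Ratio | Too narrow by | Coverage | IPD ratio |
|---|---|---|---|---|---|
| 0 | 0.0066 / 0.0066 | 1.00 | 0% | 95% | 1.00 |
| 1 | 0.0067 / 0.0078 | 1.17 | 14% | 91% | 1.00 |
| 2 | 0.0067 / 0.0088 | 1.31 | 24% | 87% | 1.02 |
| 5 | 0.0069 / 0.0110 | 1.59 | 37% | 78% | 1.03 |
| 10 | 0.0072 / 0.0138 | 1.92 | 48% | 69% | 1.07 |

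**Size in a single year**

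The ratio is about √(1 + θμ), with μ the mean episodes per person. With half a year's censoring, μ = 0.05487 × 0.98 ≈ 0.054. For θ = 1, 2 and 5 the ratios are √1.054 = 1.027, √1.108 = 1.053 and √1.270 = 1.127, so intervals are about 3%, 5% and 11% too narrow. For IPD, μ is at most 0.00183 and the effect is under 0.5% at θ = 5.

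**Upper case for IPD**

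Protocol Section 7 reports recurrence in up to 25% of patients. If exactly 25% of cases have one repeat, E[k²]/E[k] = (0.75 × 1 + 0.25 × 4)/(0.75 × 1 + 0.25 × 2) = 1.75/1.25 = 1.4. The SE ratio is √1.4 = 1.18, so intervals are about 15% too narrow. At 10% recurrence, √(1.3/1.1) = 1.09, or 8%.

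**Absolute size**

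Protocol Table 3 expects 38,848 all-cause events (VE 5%, 4% censoring, 97 months). A pooled rate then has a half-width of about 1.96/√38,848 = 1.0%, which becomes 1.2% to 1.6% for θ from 1 to 5. If one vaccination group held a quarter of the events (an assumption), 1.96/√9,712 = 2.0% would become 2.3% to 3.2%.

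**The case against.** The strongest reply is that the plan itself is right. SAP 5.8.6 states the correct estimator and the code is only an example. The block cannot run as printed, so a programmer must rework it before any output exists. The production data may also hold columns outside the example layout: the code already assumes `event`, and 7.2.4 assumes `pcv13date14`. If one of them is called `patid`, the fault becomes a visible length error. Even where clustering is lost, the affected intervals are narrow and descriptive, and every study objective concerns vaccine effectiveness.

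Most of this stands. It makes the silent failure conditional and the consequence small. It does not remove the point. Repairing `event` and `lnpy` does not lead anyone to the cluster argument, and it is the step after which the fault no longer shows. The amendment log says that the code was updated to deliver the clustering, so a programmer has reason to trust the line. No heterogeneity at all is also unlikely: the version 1.1 log entry reports implausibly many recurrent events in several patients under the earlier 30-day rule. The 90-day rule reduces such repeats but is not shown to remove them.

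**Conclusion.** The code in SAP 7.2.3 contradicts SAP 5.8.6 on the documented layout and should be corrected. It is a minor point. The failure is silent only if `event` and `lnpy` are supplied and no `patid` column exists; otherwise the code stops.

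The size rests on an assumed frailty variance. For all-cause pneumonia over full follow-up the SE ratio is 1.0 with no heterogeneity and 1.17 to 1.59 for variance 1 to 5. Single-year intervals are about 3% to 11% too narrow for the same variances. IPD intervals are 0 to about 7% too narrow at the SAP's rates for variance up to 10 (largest ratio 1.065, so 1 − 1/1.065 = 6.1%).

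A reader might infer three stronger things that the documents do not support:

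- **That the reported intervals will certainly be wrong.** The code is an example, and the production column names are not given.
- **That vaccine effectiveness is affected.** The Cox and Andersen-Gill code clusters on `ptid`. Point rates and first-event rates do not depend on the faulty line.
- **That IPD intervals would typically be 15% too narrow, or that annual rates suffer as much as full follow-up.** The 25% is an upper figure, cited to a source that the protocol describes as a trial in Malawian adults recently hospitalised with pneumonia. The 90-day rule also merges early repeats. Annual rates have too few repeat episodes per person for an effect of that size.

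**What to change.** In SAP 7.2.3, for the recurrent-event rates:

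- Create `d <- subset(ipdrec, tstart >= 0)`. Name the outcome column consistently (`ipd` or `event`) and define `lnpy` for this dataset from at-risk time as SAP 5.8.6 describes it.
- Fit both Poisson models on `d`.
- Use `vcovCL(fit, cluster = d$ptid, type = 'HC0')` in both calls. Correcting the name without restricting the rows is not enough.
- Use `ptid` throughout Appendix 7.2, replacing `patient` in the censoring-weight call and `patid` here.
- Add a check that the number of clusters equals the number of distinct patients in `d`, and stop if it does not.

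The cost is a few lines of code. No estimand, model or timeline changes; the code would simply do what SAP 5.8.6 already says.

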#### 7.2.4. Code for Standardized Differences

```
library(cobalt)
smdDataY1<-subset(ipdfirst[ipdfirst$tstart==360 &
  (ipdfirst$tstart < ipdfirst$pcv13date14 | is.na(ipdfirst$ pcv13date14)),])
#Where pcv13date14 is 14 days after the PCV13 vaccination date
covs <- subset(smdDataY1, select = c(x1, x2, ...))
#Before IPTW
smdsUn<-bal.tab(covs, treat = smdDataY1$pcv13, continuous = "std",
  binary = "std", s.d.denom = "pooled")
x1SmdUn<-smdsUn$Balance[1,2]
x2SmdUn<-smdsUn$Balance[2,2]
...
#After IPTW
smdsWt<-bal.tab(covs, treat = smdDataY1$pcv13, continuous = "std",
```

```
binary = "std", s.d.denom = "pooled", weights=smdDataY1$iptw.stab)
x1SmdWt<-smdsWt$Balance[1,3]
x2SmdWt<-smdsWt$Balance[2,3]
```

```
...
```

### 7.2.5. Code for Cox Models

```
#Code is the same for first event and recurrent events (Andersen-Gill) models
#Crude overall
library(survival)
crude.cox<-coxph(Surv(tstart, tstop, ipd) ~ pcv13 + cluster(ptid), data = ipdfirst)
```

```
#IPT weighted overall
iptw.cox<-coxph(Surv(tstart, tstop, ipd) ~ pcv13 + x1 + x2 + cluster(ptid),
                  data = ipdfirst), weights = iptw.stab
```

```
# Schoenfeld residuals
plot(cox.zph(iptw.cox)[1])
```

```
#Piecewise IPT weighted
library(Publish)
ipdfirst$timestrata<-ifelse(ipdfirst$tstart<1080,"0-3",
                               ifelse(ipdfirst$tstart<1800,"3-5", ifelse(ipdfirst$tstart<2550,"5-7","7+")))

iptw.cox.p<-coxph(Surv(tstart, tstop, ipd) ~ pcv13*strata(timestrata) + x1 + x2 +
                     cluster(ptid), data = ipdfirst, weights = iptw.stab)
summary(iptw.cox.p)
publish(iptw.cox.p)
```

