7. RATIONALE AND BACKGROUND

Human immunodeficiency virus (HIV) infection leads to extensive defects in the immune system, including the progressive depletion and dysfunction of CD4⁺ T cells, perturbation of the B cell compartment with reduced resting memory B cells, and suboptimal humoral immune responses [11-14]. People living with HIV (PLWH) are at increased risk of pneumococcal infections. While antiretroviral therapy (ART) can restore the immune system and consequently lower the risk of pneumococcal infections [2, 15], the burden of pneumococcal infections persists in PLWH [16, 17]. A recent meta-analysis shows that in the era of advanced ART, the incidence rate of invasive pneumococcal disease (IPD) in PLWH is approximately 30 times higher when compared with the general population [1]. Even with timely and effective treatment, the case fatality rate of IPD is at least 8% in PLWH [2]. Up to 25% of PLWH experience recurrent episodes of IPD in the subsequent 12 months [3].

International guidelines recommend pneumococcal vaccination for immunocompromised individuals [4]. In the United States, one dose of 13-valent pneumococcal conjugate vaccine (PCV13) has been recommended to PLWH since 2012 [18]. Currently, the CDC recommends 20-valent pneumococcal conjugate vaccine (PCV20) alone or 15-valent pneumococcal conjugate vaccine (PCV15) followed by pneumococcal polysaccharide vaccine (PPSV23) for adults aged 19-64 years with certain underlying medical conditions, including HIV infection, and for all adults aged ≥ 65 years [19].

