9.7. Data Analysis

Cox proportional hazards models will be used to estimate the hazard ratio (HR) for each outcome comparing vaccinated PLWH with unvaccinated (no PCV13) PLWH. To explore potential changes in VE over time, HRs will also be generated during specific time periods (0-3, 3-5, 5-7 years of follow-up) using piecewise Cox regression models, if there is adequate sample size. All models will be adjusted for time-fixed and time-varying covariates of interest using inverse probability of treatment weighting. The time-fixed covariates of interest include sex, age, payor, SVI, previous pneumonia infection, and hospitalization and will be measured during the baseline period. The time-varying covariates include risk factors for pneumonia (alcoholism, asplenia, asthma, chronic heart disease, kidney, liver, and lung diseases, cigarette smoking, diabetes, immunosuppressive conditions and medications, and sickle cell disease), annual physical exams, annual influenza vaccine, hospitalization, opportunistic infections, ART adherence, annual CD4 and viral load laboratory tests, and an indicator for respiratory virus season.

VE will be calculated as 1 minus the estimated HR for each outcome.

We will conduct two sets of analyses for each outcome. In the first set, we will examine the first event for each outcome and in the second set, all recurrent outcome events during follow-up will be included. In the first set of analyses, unvaccinated (no PCV13) PLWH will be followed from index date until the earliest occurrence of the following: outcome, PCV13 vaccination, death, end of health plan enrollment, or end of study period, and vaccinated PLWH will be followed from 14 days after vaccination date, or index date if vaccinated during the baseline period, until the earliest occurrence of outcome, death, end of health plan enrollment, or end of study period. In the second set of analyses unvaccinated (no PCV13) PLWH will be followed from index date until the earliest occurrence of PCV13 vaccination, death, end of health plan enrollment or end of study period and vaccinated PLWH will be followed from 14 days after vaccination date, or index date if vaccinated during the baseline period, until earliest occurrence of death, end of health plan enrollment, or end of study period.

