### 5.3.2. Covariates

The list of demographic and clinical characteristics considered for descriptive reporting, subgroups and inclusion as covariates in models for generating the propensity scores are provided in Table 5.3. The Komodo Health database will be source of all variables.

Patients will be considered to have a comorbidity or hospitalization during baseline if there was evidence of a diagnosis at any time during the baseline period. Evidence of comorbidities or hospitalization during follow-up will be considered as new diagnoses. Once diagnosed, patients will be considered diagnosed for the remainder of their follow-up. ART adherence during baseline and follow-up will be updated every 6 months (180 days) based on the data collected in that previous timeframe. For baseline annual physical exam and annual influenza vaccine, patients will be considered adherent (coded as 'Yes') if there was evidence of these events at any time during the baseline period. During the follow-up, patients will be considered adherent up to 365 days after the last event date.

For annual CD4 and viral load laboratory tests during baseline and follow-up, patients will be coded as 'Yes' up to 365 days after the last event date. For respiratory virus season during follow-up, patients will be coded as 'Yes' if the observation time is in October, November, December, January, February, March or April.

The baseline period for the assessment of covariates is the six months prior to the index date, i.e., no data prior to six months will be included.

Covariates used at baseline only will be considered time-fixed confounders. Covariates additionally or only used during follow-up will be considered time-varying confounders.

Categories may be collapsed, or covariates may be excluded from the propensity scores if models fail to converge.

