**Table 5.3 List of Covariates**

Variable	Operational Definition	Role	Time of Use
Age in years	Calculated as [year individual meets HIV criteria] – [birth year]  Categorized as: 18-49, 50-64, 65-74, and $\geq 75$ years  As a subgroup, age will be categorized as 18-49, 50-64 and 65+ years	Descriptive (continuous and categorical)  Covariate (categorical)  Subgroup (categorical)	Baseline
Sex	Male, Female, Other/ Unknown	Descriptive, covariate	Baseline
Social Vulnerability Index (SVI)	SVI characterizes resiliency of a community when faced by external pressures and stresses[6, 7]. SVI ranges from 0 to 100, where a value of 100 indicates the most vulnerable population.  3-digit zip codes will be translated to 3-digit zip code tabulation areas, and SVI will be calculated at the 3-digit zip code tabulation area.  Categorized as: low (lowest quartile), average (middle two quartiles) and high (highest quartile).	Descriptive, covariate	Baseline
US region	Northeast, North Central, South, West, Unknown	Descriptive, covariate	Baseline

Payor	Commercial, Dually eligible, Medicaid/CHIP, Medicare, Missing, Other	Descriptive, covariate	Baseline
Year of HIV diagnosis	Calendar year of first HIV diagnosis code 2014, 2015, 2016, 2017, 2018, 2019, 2020, 2021.  When used as a subgroup year will be categorized as 2014, 2015-2016, 2017-2018, 2019-2021.	Descriptive, covariate, subgroup	Baseline
Alcoholism	ICD-9-CM or ICD-10-CM codes listed in Appendix Protocol Annex Table 1.1 Yes, No	Descriptive, covariate	Baseline and follow-up
Asplenia	CPT/Healthcare Common Procedure Coding System (HCPCS), ICD-10-Procedure Coding System (ICD-10-PCS), ICD-9-Procedure Coding System (ICD-9-PCS), ICD-9-CM, or ICD-10-CM codes listed in Protocol Annex Table 1.2	Descriptive, covariate	Baseline and follow-up
Chronic heart disease	CPT/HCPCS, ICD-10-PCS, ICD-9-PCS, ICD-9-CM, or ICD-10-CM codes listed in Protocol Annex Table 1.4 Yes, No	Descriptive, covariate	Baseline and follow-up
Chronic kidney disease and renal failure	CPT/HCPCS, ICD-10-PCS, ICD-9-PCS, ICD-9-CM, or ICD-10-CM codes listed in Protocol Annex Table 1.5 Yes, No	Descriptive, covariate	Baseline and follow-up
Chronic liver disease	CPT/HCPCS, ICD-10-PCS, ICD-9-PCS, ICD-9-CM, or ICD-10-CM codes listed in Protocol Annex Table 1.6 Yes, No	Descriptive, covariate	Baseline and follow-up
Chronic lung disease	ICD-9-CM or ICD-10-CM codes listed in Protocol Annex Table 1.7 Yes, No	Descriptive, covariate	Baseline and follow-up

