#### **5.8.7. Vaccine Effectiveness**

Crude PCV13 VE percentages will be estimated based on  $(1-HR) \times 100$ , where HR is obtained from unadjusted Cox models for first episodes for each outcome. VE percentages will also be obtained from marginal structural Cox models (Cox-MSM) after applying the IPT and the IPT\*IPC weights. As the numerators for the stabilized weights will include the index-fixed covariates, those covariates will also be included in the Cox-MSM for the outcomes [9]. Cluster robust standard errors will be used to account for the multiple records per patient. The proportional hazards assumption will be assessed graphically with the inspection of Schoenfeld residuals.

To explore potential changes in VE over time, HRs may also be generated during specific time periods using piecewise Cox models. The time periods will be 0-3 years (0 to 1079 days), 3-5 years (1080 to 1799 days), 5-7 years (1800 to 2549 days).

VE may also be assessed for recurrent events using the Andersen-Gill (AG) model [11]. For each outcome, subsequent events will be of the same type, e.g., in the analysis of IPD it will be assumed that a patient is only at risk for future IPD events. The VE is assumed constant across the recurrent events.

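### The exploratory piecewise VE model has no term for the calendar period of follow-up, so all-cause pneumonia VE can appear to change between years 3-5 and 5-7 when it is constant

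*SAP*

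**What the plan says.** The time axis of every Cox model in SAP 7.2.5 is days since index. SAP 5.8.7 says that "HRs may also be generated during specific time periods using piecewise Cox models", for days 0-1079, 1080-1799 and 1800-2549. The example code is "coxph(Surv(tstart, tstop, ipd) ~ pcv13*strata(timestrata) + x1 + x2", so each baseline covariate has one coefficient across all windows.

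Two variables carry calendar time:

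- **Index year.** SAP Table 5.3 defines it as "Calendar year of first HIV diagnosis code 2014, 2015, 2016, 2017, 2018, 2019, 2020, 2021". SAP 5.3.2 adds that "Covariates used at baseline only will be considered time-fixed confounders", and SAP 5.8.7 that "those covariates will also be included in the Cox-MSM for the outcomes". It is therefore a main effect in the outcome model. Under SAP 5.8.4 it is in both numerator and denominator of the stabilized weights.
- **Season.** An October-April indicator, the same in every year. As a time-varying covariate it is lagged by one interval and enters only the weight denominators.

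No variable records the calendar period in which follow-up time falls. VE by index year is planned for the first three years of follow-up only (Protocol 9.7, SAP 5.2.3).

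**The concern.** A given window covers different calendar periods for different index cohorts. For an index in mid-2014, years 3-5 run from about mid-2017 to mid-2019. For an index in mid-2017 they run from about mid-2020 to mid-2022. A change in incidence confined to 2020-2022 therefore reaches different cohorts in different windows. One index-year coefficient, averaged over all windows, cannot follow it. If those cohorts also differ in PCV13 coverage at the same time since index, the misfit is pushed into the window-specific PCV13 coefficients.

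The incidence condition has a basis in the documents: SAP Table 7.4 counts J12.82 (COVID-19 pneumonia) as all-cause pneumonia, a primary outcome. VE at 3, 5 and 7 years, if feasible, is named in each objective. A late rise in incidence would look like waning, and a late dip like increasing protection. No planned analysis would tell these apart: VE by index year stops before the affected windows, and Schoenfeld residual plots cannot separate true waning from a calendar artefact.

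**Working it through.** **1. Reproducing the plan's precision.** Protocol Table 2 (97 months, 4% censoring, VE 22.5%) gives 11 to 33. The SE of log HR is [ln(0.89) - ln(0.67)] / 3.92 = 0.0724. For 58,000 people it is 0.0724 x sqrt(175,000/58,000) = 0.126, which gives a VE interval of 0.8 to 39.4. SAP Table 5.1 states 1 to 40. The rows for 87,000, 43,000 and 22,000 also agree within 2 points.

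**2. Calendar position of the windows.** The earliest first code is January 2014, so the earliest index is about July 2014. Day 1080 is 2.96 years later (mid-2017) and day 1800 is 4.93 years later (mid-2019). Both windows can run to 30 September 2022.

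**3. Expected-count cohort.**
- From the documents: 175,000 people, 32% vaccinated, 4% annual censoring, all-cause pneumonia 5,487 per 100,000, end of study 30 September 2022, true VE 15% in every window.
- Assumed: entry (uniform over 2014-2021, or 40% in 2014), uptake over calendar time, and incidence over calendar time. No other confounding is simulated, so all weights are 1.
- Planned model: Poisson regression with a free baseline per 30-day interval (equivalent to Cox on time since index), index-year main effects and PCV13 by window. It is then refitted with calendar quarter added.

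All-cause pneumonia, 40% entering in 2014:

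| Uptake | Incidence | VE 0-3 / 3-5 / 5-7 | 5-7 minus 3-5 | With quarter |
|---|---|---|---|---|
| Steep fall | flat | 15.0 / 15.0 / 15.0 | 0.00 | 0.00 |
| Steep fall | -10% per year | 14.9 / 14.8 / 14.8 | -0.03 | -0.02 |
| Rise then fall | x2, Apr 2020-Feb 2022 | 15.3 / 14.8 / 14.3 | -0.44 | +0.02 |
| Moderate fall | x1.5, Apr 2020-Feb 2022 | 14.9 / 15.6 / 14.5 | -1.09 | +0.01 |
| Moderate fall | x2, Apr 2020-Feb 2022 | 14.9 / 16.0 / 14.2 | -1.80 | +0.02 |
| Moderate fall | x0.5, Apr 2020-Jun 2021 | 15.1 / 14.9 / 16.5 | +1.63 | 0.00 |
| Steep fall | x2, Apr 2020-Feb 2022 | 15.0 / 18.0 / 13.5 | -4.48 | +0.04 |
| Steep fall | x0.5, Apr 2020-Jun 2021 | 14.9 / 14.3 / 17.9 | +3.56 | 0.00 |

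With flat uptake the false change is 0.05 points or less whatever the incidence. A log-linear trend is harmless because calendar time is index time plus time since index, and the model has terms for both. The largest case over both entry patterns shows 16.2% and then 10.5%, a false fall of 5.7 points. Differently drawn curves give up to 0.6 points for rise-then-fall uptake, 0.7-1.2 for a fall from 2020 and up to 7.0 for a steep fall throughout.

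**4. Sampling error of the difference.** Treating the windows as independent, the half-width is about 1.96 x HR x sqrt(SE1^2 + SE2^2).
- All-cause pneumonia, moderate fall, x1.5: 1.96 x 0.85 x sqrt(0.022^2 + 0.024^2) = 5.4 points. With the x0.5 dip: 1.96 x 0.85 x sqrt(0.024^2 + 0.032^2) = 6.7 points. Over all scenarios it is about 5-8.
- IPD, moderate fall, x0.5 dip: 1.96 x 0.775 x sqrt(0.124^2 + 0.156^2) = 30 points. The corresponding false IPD changes are +0.8 to +1.6 points (moderate fall) and +1.7 to +3.9 (steep fall), for dips of x0.7 to x0.5.

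**The case against.** The strongest reply is that the size rests on uptake curves that the documents do not contain. They give one figure, 32% ever vaccinated. Protocol section 7 says "Currently, the CDC recommends 20-valent pneumococcal conjugate vaccine (PCV20) alone or 15-valent", but the source cited for this is dated 2022 and the study ends in September 2022. A reader might infer a long decline in PCV13 uptake from it; it does not show one. A fall confined to 2022 gives a false change of 0.13 points or less. This part stands: the larger figures are conditional.

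The windows are also exploratory and depend on adequate sample size, and most of the false changes lie within the sampling error of the difference. That limits the priority. It does not remove the point: no hypotheses are tested, so readers will compare point estimates, and an assumed all-cause VE of 5-15% leaves little room for an error of several points.

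The secondary outcomes offer a partial comparison, since SAP Table 7.5 does not list J12.82. They are different outcomes and do not repair the all-cause windows.

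A reader might also infer that index year is left out altogether, because Protocol 9.7 says "The time-fixed covariates of interest include sex, age, payor, SVI" and its list does not name it. Protocol Table 1 and SAP Table 5.3 both include it, so this mismatch is editorial.

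**Conclusion.** The concern holds for the windowed all-cause pneumonia VE. With constant true VE, the planned piecewise model can show a false change between years 3-5 and 5-7. Two conditions are needed together: incidence that changes non-log-linearly over calendar time, and PCV13 uptake at the same time since index that differs between index cohorts.

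The size is about 0-0.6 points for flat or rise-then-fall uptake, about 1-2 points for a gradual fall or a fall from 2020, and about 3-7 points for a steep fall throughout, against a half-width of about 5-8 points. These are bands over assumed curves and not predictions.

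It would be tempting to conclude that the main VE estimates are biased, or that IPD durability cannot be read. The calculations do not support either: overall VE moves by 0.6 points or less, and the IPD error is small beside an interval of about 30 points either side. The change is worth making because it is cheap and nothing else planned would reveal the problem.

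**What to change.** Derive a time-varying calendar quarter for each person-time record, unlagged because vaccination cannot affect it. The 30-day records cross quarter boundaries, so either split them or assign the quarter at interval start.

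- **Outcome model.** Add calendar quarter to the SAP 7.2.5 piecewise formula as its own term, for example a separate `strata(calq)`, and leave the PCV13-by-window interaction as it is. Do not merge quarter into the window strata term: that would interact PCV13 with every window-quarter cell and give no single VE per window.
- **Weights.** Add quarter to the numerator and denominator of the IPTW and IPCW models. Keep the October-April covariate, which the protocol lists and which quarters do not reproduce, because April and May-June share a quarter.
- **Scope.** Apply this at least to the windowed all-cause pneumonia VE.
- **Editorial.** Add index year to the Protocol 9.7 covariate list, to match Protocol Table 1 and SAP Table 5.3.

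The cost is row splitting and regenerating the weights for the analyses concerned, with a negligible loss of precision. Tabulating PCV13 uptake and outcome incidence by calendar quarter would also show whether the two conditions are met.
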